- Week 5: Increase dose by 5 mg/kg/day for total daily dose of 25 mg/kg/day; subject will be evaluated here

If a subject responds well to an intermediate dose during the Core Phase, he or she may be maintained at that dose and does not need to complete escalation. Escalation may resume during the Optimization or Extension Phase if there is a temporary increase in seizures. If escalation resumes, the dose will be increased by 5mg/kg/day at each visit up to a maximum of 25mg/kg/day.

The dose of concomitant anti-epileptic drugs will remain unchanged during the first 14 weeks of CBD treatment (or until 8 weeks after steady state at final dose), unless symptoms of toxicity and/or significant changes in blood levels are observed.

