### Laboratory tests and clinical procedures

- Weight, vitals and orthostatics will be monitored at baseline and at each visit. For subjects who are physically unable to complete standing orthostatics, only supine orthostatics will be collected. (Routine care)
- Neuroscores will be assigned at each visit by [name] as per her clinical routine. Neurologic exam and general physical exam will also be performed at each visit. (Routine care)
- Participants will be asked at each clinic visit about migraine frequency, severity (scale of 1-10) and duration, and any change in neurologic symptoms
- CBC, LFT, BUN, creatinine levels, electrolytes, will be measured at baseline, one month after baseline, one month and two months after maintenance dose steady state is reached, every 2-3 months during the Optimization Phase, and every three months (at each visit) during extension phase. Urine analysis will be performed at each of the extension phase visits (every three months).
- For subjects with a facial port-wine birthmark, frontal and profile photograph will be taken under standardized conditions with scoring of the port-wine birthmark for percent of face covered, thickness of birthmark, and darkness of birthmark color. Subjects without any facial port-wine birthmark will only need photographs taken at a single visit to confirm the lack of birthmark. (Research, See Study Visit Table)
- Concomitant AED plasma concentrations will be measured at baseline, one month after baseline, at steady state maintenance CBD dose, one month and two months after maintenance dose steady state is reached, every 2-3 months during the Optimization Phase, and at each extension phase visit.
- CBD plasma concentrations will be measured twice, at 6 and 10 weeks after baseline.
- hCG urine pregnancy test will be used for all female participants Tanner stage 2 and above (see Study Visit Table). We will tell subjects that they must be using effective birth control (for example, abstinence, birth control pills, contraceptive implants, condoms) and confirm that this is the case at each study visit. We will inform female subjects that they should not become pregnant or breastfeed a baby while on this study or for 30 days after taking Cannabidiol. We will also inform male subjects that they should not get their partners pregnant while on this study or for 30 days after taking Cannabidiol. Anyone who becomes pregnant while on the study will be removed immediately.

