## 2. Study Visits:

- Study Visit 1: Screening Visit: Informed consent process, eligibility criteria, provide seizure diary and instruct on use.
- Study Visit 2: Baseline Visit: Confirm eligibility and begin drug at dose 1 (see Visit Table and Dose Schedule). Provide study drug dosing record and instruct on use.

During the following Study Visits (see Visit Table), the participants will undergo clinical assessments, a neuroscore, have pictures taken, blood draws for laboratory tests, study drug accountability, concomitant medication survey, adverse event reporting, and study drug administration (see Visit Table for details).

An additional blood draw will also be necessary within 72 hours of a previous blood draw if the most recent result indicates a clinically significant ( $>3xULN$ ) elevation of ALT or AST. At minimum, the following tests should be repeated: ALT/AST, total bilirubin, and alkaline phosphatase. A GGT test will also be performed at that time. This bloodwork (ALT/AST, total bilirubin, and alkaline phosphatase and GGT test) will also be necessary if: 1) the dose of your study drug dose is increased after the escalation phase, 2) another drug which affects liver function is added, stopped, or has a dose change, or 3) you have one or more of the following symptoms without another explanation: fatigue, encephalopathy, nausea, vomiting, right upper quadrant pain or tenderness, abdominal pain or distension, fever, excessive bruising, excessive nose or gum bleeds, or petechia. All trial subjects with elevated LFTs will be followed closely until all abnormalities return to the baseline state as assessed by the investigator with  $AST/ALT < 3x ULN$  and will be followed until ALT/AST have normalized and symptoms resolve.

At the end of the Core Phase (Visit 10) and Optimization Phase (visit 14), participants will have the option between continuing in an extension study or weaning off of the study drug. Those who decide to continue will remain on the same dosage of medication and return for labs and clinical visits at least every three months or as deemed clinically necessary, and drug will be provided free of cost to the subject for at least one year, or until the drug is approved for clinical use for the treatment of epilepsy in patients with Sturge-Weber syndrome. Those who decide to wean off of the study will return for a final follow-up visit in 1 month (Week 52).

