**Treatment will continue until any of the following take place:**

1. Loss of seizure control defined as an increase of 50% in the average weekly number of seizures for a minimum of 4 weeks as compared to the average weekly number of partial-onset seizures during the 8 weeks baseline period. At this point, the subject's CBD dose can be decreased without requiring immediate withdrawal. The subject does not need to be withdrawn unless the seizure frequency does not drop below the 50% increase on the lowered dose.
2. Use of rescue medications longer than the maximum duration determined during the Baseline period.
3. Intolerable toxicity.
4. Treatment failure as defined above.
5. Pregnancy.
6. Withdrawal of consent.
7. Treatment duration completed as per protocol: completion of the Core phase (if patients do not accept to start the extension phase) or completion of the Extension phase.
8. Laboratory results indicate that the subject's liver function test (ALT or AST) has increased in any of the following ways:
  - >8xULN
  - >5xULN for more than 2 weeks
  - >3xULN **and** either (TBL >2xULN **or** INR >1.5)
  - >3xULN with the appearance of fatigue, nausea, vomiting, right upper quadrant pain or tenderness, fever, rash, and/or eosinophilia (>5%)

*g. Description of what happens to participants receiving therapy when study ends or if a participant's participation in the study ends prematurely.*

At study's end GW Pharmaceuticals will continue to provide drug to any patient doing well on Epidiolex and wanting to remain on it (extension study), at least until they have obtained an indication for pediatric epilepsy and it can be billed to the patient's insurance company. All others will be weaned off of the study drug over a month and seen back for one final follow-up visit one month later. For those discontinued specifically due to elevated liver function tests, they will continue to be followed until all abnormalities return to the baseline state as assessed by the investigator with AST or ALT <3xULN. Any patient removed early from the study, and all participants at the end of the study wishing to remain

**PROPRIETARY MATERIALS OF THE HUGO W. MOSER RESEARCH INSTITUTE AT KENNEDY KRIEGER, INC. DO NOT USE OR DISCLOSE WITHOUT PERMISSION OF THE RESEARCH INSTITUTE**

[name] patient will continue to be cared for by [name] and seen at the Hunter Nelson Sturge-Weber Center.

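### Rash with raised ALT/AST ends treatment, but rash alone does not prompt the liver test that would show it

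*Combined protocol and SAP*

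**What the plan says.** Two parts of Section 4 have to work together.

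- **Stopping rule.** Section 4f (Treatment will continue until any of the following take place), item 8, gives four liver criteria for ending treatment. The fourth is ALT or AST above three times the upper limit of normal (ULN) "with the appearance of fatigue, nausea, vomiting, right upper quadrant pain or tenderness, fever, rash, and/or eosinophilia", with eosinophilia set at more than 5%.
- **Unscheduled liver bloodwork.** Section 4b, Study Visits, requires a repeat draw within 72 hours "if the most recent result indicates a clinically significant" elevation of ALT or AST. It also requires the bloodwork in three other situations: (1) "the dose of your study drug dose is increased after the escalation phase"; (2) some other medicine with hepatic effects is started, withdrawn or re-dosed; (3) "you have one or more of the following symptoms without another explanation". The symptoms under (3) are "fatigue, encephalopathy, nausea, vomiting, right upper quadrant pain or tenderness, abdominal pain or distension, fever, excessive bruising, excessive nose or gum bleeds, or petechia".

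Routine liver panels are set in Section 4a, Laboratory tests and clinical procedures. They "will be measured at baseline, one month after baseline, one month and two months after maintenance dose steady state is reached", then every 2 to 3 months in the Optimization Phase and every 3 months in the Extension Phase.

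**The concern.** Item 8 depends on a laboratory value, so nobody can apply it until blood is drawn. For most of the clinical signs it names, the plan closes the loop: the sign appears, bloodwork is required, and the result decides whether the drug stops. Rash breaks that chain. The protocol treats rash with a raised transaminase as reason enough to stop, yet rash alone does not oblige anyone to measure the transaminase. A subject could meet a stopping criterion and stay on drug until a panel happens to fall due. What is at stake is how promptly the plan's own safety rule is applied. No efficacy or safety estimate depends on it.

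**Working it through.** **Step 1: compare the two lists.**

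| Sign in the item 8 symptom criterion | Prompts unscheduled bloodwork under Section 4b? |
|---|---|
| Fatigue | Yes |
| Nausea | Yes |
| Vomiting | Yes |
| Right-upper-quadrant pain | Yes |
| Fever | Yes |
| Rash | **No** |
| Eosinophilia (laboratory value) | No |

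Five of the six clinical signs are triggers and rash is the only exception. Eosinophilia is also absent, but it is itself a blood result, and the routine blood count is scheduled together with the liver panel. The trigger list is closed: it has ten entries and no wording that makes them examples. Petechia is the nearest skin sign and does not cover rash in general. Nothing elsewhere in the protocol ties rash to a liver test.

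**Step 2: check whether another trigger fills the gap.**

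- The 72-hour repeat needs a previous result already above 3xULN.
- Trigger 1 applies only to dose increases made after escalation. The planned step "Week 5: Increase dose by 5 mg/kg/day for total daily dose of 25 mg/kg/day" is part of escalation, so it prompts no draw.
- Trigger 2 needs a change in another drug that affects the liver. Section 4a holds the other anti-epileptic drugs fixed for the first 14 weeks unless there is toxicity or a significant change in levels, so this will be uncommon in the Core Phase. It is more likely in the Optimization Phase, when those drugs may be adjusted.

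**Step 3: reconstruct the Core Phase panel dates.** The Study Overview in Section 4a gives weekly evaluations for 6 weeks, then visits 4 and 8 weeks later. Counting Visit 2 as week 0, Visits 6, 8, 9 and 10 fall at weeks 4, 6, 10 and 14. Two statements agree with this: CBD levels are due at 6 and 10 weeks (Section 4a) and at Visits 8 and 9 (Section 8b, item 6). Taking a month as 4 weeks and steady state as reached at week *s*, the panels fall at weeks 0, 4, *s* + 4 and *s* + 8, so the gaps are 4, *s* and 4 weeks.

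- *s* = 6, as implied by pairing 14 weeks of treatment with 8 weeks after steady state: panels at 0, 4, 10 and 14; gaps 4, 6, 4; longest wait 6 weeks.
- *s* = 5, if steady state is counted from the week 5 dose: panels at 0, 4, 9 and 13; gaps 4, 5, 4; longest wait 5 weeks.

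With *s* = 6, the 6-week gap from week 4 to week 10 contains the week 5 step to 25 mg/kg/day and the first 10 − 5 = 5 weeks at that dose.

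**Step 4: average wait.** If rash is equally likely to begin at any time and nothing else prompts a draw, the mean wait is the sum of squared gaps divided by twice the total time:

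(4² + 6² + 4²) / (2 × 14) = 68 / 28 = 2.43 weeks.

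For equally spaced panels the maximum wait is the interval and the mean is half of it.

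| Phase | Panel interval | Longest wait | Mean wait |
|---|---|---|---|
| Core (*s* = 6) | 4, 6, 4 weeks | 6 weeks | 2.4 weeks |
| Optimization | 2–3 months = 8.7–13 weeks | about 9–13 weeks | 4.3–6.5 weeks |
| Extension | 3 months = 13 weeks | about 13 weeks | 6.5 weeks |

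These are waits to a mandated test. They become delays in stopping only if ALT or AST is above 3xULN at the same time and none of the ten listed symptoms is present. The documents give no rate for either rash or such an elevation.

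**The case against.** The strongest reply is that the lists serve different purposes. One says which unexplained symptoms justify a draw; the other says which signs make an already known elevation serious enough to stop. A sign can matter for the second and not the first, the lists differ in both directions, and both sections can be followed as written. The other three criteria in item 8 name no symptom at all, so a symptom-free subject above 8xULN also waits for the next panel.

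Clinical oversight is also close. Subjects are seen weekly for 6 weeks, assessed at each visit and at phone or email contact (Section 7c), monitored for side effects and able to reach the investigator directly (Section 8b). In a 10-subject study run by one specialist, that judgement is a real safeguard.

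Finally, the calendar is a reconstruction. A subject held at an intermediate dose reaches steady state earlier and has a shorter middle gap; slower titration lengthens it. Uniform onset is a convenience, and the Optimization figures ignore draws prompted by changes in other drugs.

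Much of this stands as a limit on size. The two texts do not contradict each other, testing is not barred, and the waits are nominal. It does not remove the gap. The plan chose to mandate testing for ten symptoms although discretion was available for those too, and it gives no reason for treating rash differently from fever or fatigue in the same criterion. That symptom-free elevations wait for a panel is unavoidable; rash is a visible sign that the plan itself regards as relevant.

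**Conclusion.** The point holds, as a minor gap in safety monitoring. That rash is the one clinical sign in the item 8 symptom criterion without a matching test requirement follows directly from the text. The size is less firm. The 6-week Core Phase maximum and 2.4-week mean rest on steady state at week 6, 4-week months and, for the mean, uniform onset with no other prompt for a draw. The later waits of up to about 9 to 13 weeks follow from the stated panel intervals under the same no-other-prompt condition. How many of the 10 subjects would be affected cannot be worked out from the documents.

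**What to change.** Add rash to the symptoms under trigger 3 in Section 4b, Study Visits. The existing qualifier, which excludes symptoms that have another explanation, would confine the draws to unexplained rash. Item 8 of Section 4f needs no change: every clinical sign in its symptom criterion would then prompt the test needed to apply it. The cost is one word in the protocol and, at most, a few extra blood draws among 10 subjects.

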## 5. Inclusion/Exclusion Criteria

**Inclusion criteria:** Participants with Sturge-Weber syndrome brain involvement as defined on neuroimaging (n=10 subjects, male and female, ages 1 month to 45 years of age) and the following:

1. Documentation of a diagnosis of drug resistant epilepsy as evidenced by failure to control seizures despite appropriate trial of two or more AEDs at therapeutic doses. **Drug resistant epilepsy for this study is defined as:** At least 1 reported quantifiable (no cluster or innumerable) defined seizure with motor signs per month for at least 3 months prior to initial visit and during the period between Visit 1 (Screening Visit) and Visit 2 (Baseline Visit), as per data captured in daily seizure diaries. These can be focal seizures, focal seizures with impaired consciousness, myoclonic seizures, generalized, and secondarily generalized seizures.
2. Between 1-5 baseline anti-epileptic drugs at stable doses for a minimum of 4 weeks prior to enrollment. Vagus nerve stimulator (VNS), ketogenic diet and modified Atkins diet do not count toward this limit.
3. VNS must be on stable settings for a minimum of 3 months prior to enrollment.
4. If on ketogenic or Atkins diet, must be on stable ratio for a minimum of 3 months prior to enrollment.
5. Previous subjects who failed at any point to meet continuation criteria and withdrew early may be considered for re-enrollment under a new subject ID as long as the above inclusion criteria are met. The determination of whether to re-enroll will be made by the PI and sponsor on a case-by-case basis. Re-enrollment can occur no earlier than 4 weeks after the final, post-weaning follow-up visit under the old subject ID.

Written informed consent obtained from the patient or the patient's legal representative must be obtained prior to beginning treatment.

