#### 4. Study Procedures

a. *Study design, including the sequence and timing of study procedures (distinguish research procedures from those that are part of routine care).*

**Study Overview:** Investigator Initiated Expanded Access Study in 10 participants with Sturge-Weber syndrome brain involvement, medically refractory seizures and [name] participants at the Hunter Nelson Sturge-Weber Center at the Kennedy Krieger Institute

We hope to gain an understanding of the utility of pure CBD use for the treatment of drug resistant epilepsy in Sturge-Weber syndrome in this open-label dose-finding observational study. A baseline seizure frequency will be recorded for each subject in a diary for eight weeks prior to investigational drug initiation and parents/caregivers will document seizures on a daily basis throughout the study period (see seizure log). Investigational drug (CBD) will be administered as an adjunct to all current anti-epileptic drugs. All subjects will, at minimum, be clinically evaluated at screening, baseline, weekly for the first 6 weeks after drug initiation, then 4 weeks and 8 weeks later during the Core Phase. During the Optimization Phase they will be followed every 6-12 weeks (see Study Visits Table for precise timeline).

PROPRIETARY MATERIALS OF THE HUGO W. MOSER RESEARCH INSTITUTE AT KENNEDY KRIEGER, INC. DO NOT USE OR DISCLOSE WITHOUT PERMISSION OF THE RESEARCH INSTITUTE

**Method of administration:** Cannabidiol oral solution 100 mg/ml will be administered orally. The participants will be treated on an outpatient basis and will not require inpatient hospital admission.

**Dose / titration schedule:** Initiation of treatment will begin with 2 mg/kg/day given in two divided doses. The dose will be increased by 3 mg/kg/day after seven days and then by 5 mg/kg/day every seven days up to a maximum dose of 25 mg/kg/day given. The dosing schedule will be as follows, as tolerated:

- Start of study : 2 mg/kg/day; subject will be evaluated here
- Week 1: Increase dose by 3 mg/kg/day for total daily dose of 5 mg/kg/day; subject will be evaluated here
- Week 2: Increase dose by 5 mg/kg/day for total daily dose of 10 mg/kg/day; subject will be evaluated here
- Week 3: Increase dose by 5 mg/kg/day for total daily dose of 15 mg/kg/day; subject will be evaluated here
- Week 4: Increase dose by 5 mg/kg/day for total daily dose of 20 mg/kg/day; subject will be evaluated here

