#### **Measurement of changes in seizures (Routine)**

Change in seizure frequency is the primary outcome measure for this pilot trial. All seizure types will be classified before study entry. Seizure frequency for each seizure type will be recorded during a baseline of 8 weeks before administration of CBD. Seizure type, frequency will be monitored during baseline and treatment as recorded in a patient diary (see seizure log). For assessing the efficacy of CBD, the investigator will count the change in the frequency of seizures (i.e., tonic seizures, clonic seizures, tonic-clonic seizures lasting more than 3 seconds, focal motor seizures, focal seizures with impaired consciousness, atonic seizures, myoclonic seizures including myoclonic absences). In addition, parents/caregivers will report the following **secondary outcome measures**:

- Change in average seizure duration by seizure type
- Change in the number of episodes of status epilepticus, defined as convulsive seizure lasting longer than 10 minutes
- Change in the number of uses of rescue medication
- Change in the number of ER visits/ hospitalizations

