### *c. Blinding, including justification for blinding or not blinding the trial, if applicable.*

During this pilot expanded access study, where the primary objectives are to assess tolerability and dose, blinding is not appropriate. There is no placebo or non-treatment group that would require blinding.

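### The diary weeks that test entry also appear to be the outcome baseline, so with no control group a before/after seizure comparison leans toward benefit if rates are low or highly variable

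*Combined protocol and SAP*

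**What the plan says.** - **Outcome.** Section 4a: "Change in seizure frequency is the primary outcome measure for this pilot trial"; efficacy is assessed when "the investigator will count the change in the frequency of seizures". Section 7a names only seizure frequency. Section 7 gives no treatment window, summary measure or sensitivity analysis.
- **Baseline.** Section 4a: "A baseline seizure frequency will be recorded for each subject in a diary for eight weeks prior to investigational drug initiation".
- **Entry test.** Section 5, inclusion criterion 1, sets the threshold: "At least 1 reported quantifiable (no cluster or innumerable) defined seizure with motor signs per month". The same criterion applies it to two stretches of time, one before screening and one after: "for at least 3 months prior to initial visit and during the period between Visit 1 (Screening Visit) and Visit 2 (Baseline Visit". The source is the daily diaries.
- **Timing.** Section 4b, Visit 1: "Screening Visit: Informed consent process, eligibility criteria, provide seizure diary and instruct on use". At Visit 2 eligibility is confirmed and drug is started.
- **Control.** Section 4c: "There is no placebo or non-treatment group that would require blinding".
- **Other anticonvulsants.** Section 4a: their doses "will remain unchanged during the first 14 weeks of CBD treatment (or until 8 weeks after steady state at final dose"), apart from changes for toxicity or blood levels. Section 4b lets them be adjusted for better seizure control in the Optimization Phase.
- **Use of results.** Section 7c says that promising results will feed the sample size calculation for later studies.

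**The concern.** The diary starts at Visit 1 and drug starts at Visit 2, so the weeks that decide entry appear to be the weeks that supply the baseline. Too few seizures before drug can exclude a subject, while too few seizures on drug are simply counted. Among those enrolled, baseline is therefore higher on average than the true rate, and the treatment period is not. A control group would carry the same selection and cancel it, but this study has none.

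The entry floor of one seizure per month admits the rates at which this matters. What is at stake is how far an uncontrolled fall in 10 subjects, or a count of subjects with a 50% fall, can be read as a drug effect, and whether an inflated effect is used to size the next study.

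**Working it through.** **Inputs from the documents:** 8-week baseline; at least 1 motor seizure per month before Visit 1 (3 months) and again between Visits 1 and 2; 10 subjects; one group. No planned effect, alpha or power is stated, so there is no plan figure to reproduce.

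**Assumptions:** no drug effect; constant true rate L per 4-week month; independent months; 8 weeks of baseline against 8 weeks of treatment; counts Poisson, or negative binomial with dispersion a = 0.5 or 1. Triples below are in that order.

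**Step 1. One rate, at least 1 seizure required in each month.** Let P0 be the chance of a month with no seizure: exp(−L) for Poisson, (1 + aL)^(−1/a) otherwise. The expected baseline month among those enrolled is L/(1 − P0) and the expected treatment month is L. The ratio is 1 − P0, so the apparent fall is P0.

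| L per month | Poisson | a = 0.5 | a = 1 |
|---|---|---|---|
| 1 | 36.8% | 44.4% | 50.0% |
| 2 | 13.5% | 25.0% | 33.3% |
| 4 | 1.8% | 11.1% | 20.0% |
| 8 | 0.03% | 4.0% | 11.1% |

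**Step 2. One rate, weaker readings (Poisson).** If the rule means an average of 1 per month, baseline needs at least 2 in 8 weeks, and E[b | b ≥ 2] = (2L − P(1))/(1 − P(0) − P(1)). At L = 1 this is (2 − 0.2707)/0.5940 = 2.911, a fall of 1 − 2/2.911 = 31.3%. At L = 2 the fall is 7.5%. If one seizure anywhere in the interval is enough, the fall is exp(−2L): 13.5% and 1.8%.

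**Step 3. Mixes of rates.** Rates are screened equally and weighted by w, the chance of passing all five months. The pooled fall is 1 − Σ(w × L)/Σ(w × expected baseline month). For the low mix (1, 2, 3, 4 per month), Poisson, each-month reading: w = (1 − P0)^5 = 0.101, 0.483, 0.775, 0.912; the sums are 7.038 and 7.438; the fall is 5.4%. The broad mix is 1, 2, 4, 8, 16 per month.

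| Reading of the rule | Broad mix | Low mix |
|---|---|---|
| At least 1 in each month | 1.0 / 3.7 / 9.1% | 5.4 / 15.2 / 23.9% |
| Average over baseline, each of the 3 earlier months | 0.6 / 1.4 / 3.2% | 2.7 / 8.0 / 14.0% |
| Average over both periods | 1.0 / 2.2 / 4.5% | 3.7 / 9.3 / 15.3% |

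Under the each-month reading, subjects at 1 per month make up only 2–3% of the enrolled broad mix and about 4% of the low mix, so the first row of the Step 1 table describes few of those enrolled.

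**Step 4. Against sampling error.** With 10 subjects in the broad mix (each-month reading) the central 95% range of the pooled ratio is 0.79–1.23 / 0.56–1.63 / 0.44–1.80. Falls of 1.0 / 3.7 / 9.1% lie well inside it.

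**Step 5. Seizures outside the entry rule.** With m motor and o other counted seizures per month (Poisson, each-month reading), the fall is 1 − (m + o)/(m/(1 − exp(−m)) + o). With o = 2, 36.8% becomes 1 − 3/3.582 = 16.2% at m = 1, and 13.5% becomes 1 − 4/4.313 = 7.3% at m = 2.

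**Step 6. 50% responders among 10 with no drug effect** (treatment count at most half of baseline, each-month reading): 0.9 / 2.5 / 3.4 in the broad mix and 1.8 / 3.3 / 4.2 in the low mix. Without selection of the baseline, but with the same weights, they are 0.8 / 2.3 / 3.0 and 1.6 / 2.8 / 3.4.

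**The case against.** **The overlap is inferred.** The visit table was not in the text available for this check, and no section states that Visit 1 to Visit 2 is exactly eight weeks. Sections 4a, 4b and 5 are consistent with the overlap and none points elsewhere, so the inference stands, but as an inference.

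**No biased estimator is planned.** A reader might infer that the plan commits to a pooled before/after ratio. It commits to no estimator; the only numeric threshold is per subject, the 50% reduction in section 4f. The pooled ratio here only gauges size. Other summaries behave differently. Under the each-month reading the mean per-subject percent change with no effect is −29% to −39% at 1 per month, but +5% to +43% in the broad mix. That supports naming the summary in advance; it does not show that one summary is right.

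**The strict reading gives the largest figures.** A reader might take criterion 1 to exclude anyone with a seizure-free baseline month. The wording also allows an average, which roughly halves most of the mix figures, so both readings must be shown.

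**Another rule works the other way.** Exclusion criterion 3, more than 6 days of rescue medication in baseline, trims high baselines. It would seldom apply at 1–2 seizures per month, but could offset some of the effect at higher, variable rates. It is not modelled here.

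**The stakes are modest.** Section 2 gives tolerability and dose as the objective, and section 7c plans no test. This limits the weight of the point but does not remove it, because seizure frequency is the named primary outcome and may inform later studies.

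**Conclusion.** The point holds as a conditional one. If many subjects have low or highly variable seizure rates, the plan as written tilts a before/after comparison toward benefit with no drug effect. Under the assumptions above the pooled fall is about 1–9% in a broad mix and 5–24% in a low mix on the each-month reading. It is about 1–3% and 3–14% if the rule is an average over baseline, or up to about 5% and 15% if the three earlier months are averaged too. For a given motor-seizure rate it is smaller where other seizure types are also counted.

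A reader might go further and conclude that any fall seen in this study is an artefact, or that the study is invalid. The documents do not support that. They give no rates or dispersion, the bias is inside sampling error in a broad mix, and much of the expected 1–4 responders in 10 is small-count chance and not selection. This is a cheap improvement to section 7.

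**What to change.** Leave eligibility and all clinical rules unchanged. In section 7:

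1. Define the primary comparison as the 8-week baseline against the last 8 weeks of the Core Phase, before other anticonvulsants may be adjusted for better seizure control. List any change to them made within that window.
2. List every subject's baseline and treatment counts, including those who leave early, and state that baseline overlaps the entry test.
3. Beside the summary change and any count of 50% responders, give the value expected with no drug effect over a stated range of rates, dispersion and readings of the entry rule.
4. Do not carry the unadjusted effect alone into a follow-up sample size calculation.

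The choice between a pooled ratio and a median percent change is a trade-off and is left open. A likelihood conditioned on passing the entry rule is optional and corrects little when counts are overdispersed: at dispersion 1 the median no-effect ratio moves only from 0.76 to about 0.80 in the low mix.

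The cost is a little more analysis of diary data already being collected, and a headline result that may be less favourable and less certain. Ten subjects cannot pin down dispersion, so the no-effect values must be shown as a range.
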